#### **Redness**

Visual scoring of subject's skin by an expert will take place at 4 weeks (Day 29) and after skin irritation (Day 31). Scores will be on a scale from 0 to 3.

Objective scoring of the sites will also be measured using a mexameter. Triplicate recordings will be made; the average reading for each patient at each time point at each site will be used in the analysis.

Change will be calculated as post-irritation observation – 4 week observation (Day 31 – Day 29).

Secondary endpoint: Erythema index from 2d imaging will be measured at baseline and on days 15, 29 and 31.

# **Capacitance**

Triplicate measurements will be performed at each test site at baseline (Day 1) and after 4 weeks of treatment (Day 29) using a corneometer. A fourth measurement may be taken if the technician feels that one of the previous readings was abnormal. The average reading for each patient at each time point at each site will be used in the analysis. Capacitance units are reported using an arbitrary scale from 0 to 130, where values below 30 indicate very dry skin and values above 45 indicate sufficiently moisturised skin.

# Skin surface dryness (3D image)

A close-up image of each skin site will be captured using the c-cube (Pixience, France) at baseline (Day 1), after 2 weeks treatment (Day 15), after 4 weeks treatment (Day 29) and after induction of skin irritation (Day 31). Images can be analysed at the end of the study to obtain quantitative values for dryness (roughness).

### 2D Skin Imaging of Erythema

A single close-up image of each skin site will be captured using the c-cube camera with glass lens (Pixience, France). Captured 2D images are analysed to determine the skin erythema index (degree of redness, arbitrary numerical value) for the region of interest.

#### **NMF** levels

Samples for analysis of stratum corneum NMF levels will be collected by tape stripping after 4 weeks of treatment (single time point, Day 29). Two samples will be collected from each sampling site (tape-strips/discs 1-3 and 4-6), representing different depths through the stratum corneum. The samples will be analysed separately.

#### Participant tolerability VAS

Participants will use a diary to record their VAS score of the degree of smarting at the start of treatment (Day 1), after 5 days (Day 15) and again after 4 weeks (Day 29).

#### **Cream Consumption**

Cream consumption will be based on the weight of the reference and test creams before (Day 1), during (Days 5 and 15) and after use (Day 29).

#### **Adverse Events**

Participants will record AEs throughout the study in their diaries with the information transferred to the CRF at Day 29 and Day 31.

#### **FLG loss-of-function mutations**

Saliva samples will be collected at baseline (Day 1) to obtain genomic DNA for determination of participant FLG gene status. Samples will undergo DNA extraction and genotyping at the University of Sheffield for the 5 common European loss-of-function FLG mutations that have been reported to confer increased AD risk.

#### 7. Statistical Analyses

Outcome and demographic data will be summarised at each time point using appropriate descriptive statistics such as N, mean, standard deviation, min, lower quartile, median, upper quartile, max.

As noted in section 5 the data will be explored during the blind data review to assess if the proposed analysis methods needs to be updated to allow for the location or adherence of the SLS patches.

# 7.1 Primary Analysis

The primary analyses will compare the test treatment to no treatment and to the two reference creams in terms of change in TEWL and redness (visual scoring and mexameter) between days 31 and 29. This will be done using Analysis of Covariance (ANCOVA) with change (Day 31 - Day 29) as the outcome, treatment as a factor, subject as a random effect and day 29 incuded as a covariate. Key group comparisons (Miniderm Novum Vs Control, Miniderm Novum Vs Miniderm 20% and Miniderm Novum Vs Diprobase) will be calculated directly from the ANCOVA model.

These analyses will be carried out on both the FAS and the PPS, the analysis on the PPS will be considered supportive of the primary analysis carried out on the FAS.

In both analyses, if the assumptions of the test are not met, transformations of the raw data or alternative tests will be considered, such as the Wilcoxon matched pairs or sign test, and the most appropriate solution applied.

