#### 10.2 Method of Assigning Participants to Treatment Groups

Randomisation (allocation of the treatments to the test sites) will be performed according to a randomisation list with balanced allocation to the 4 different test areas (to avoid site-dependent effects). Participants eligible for the study will be provided with a participant ID number at Visit 1.

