## 13.1.4 Primary Efficacy Analysis

The primary analysis will compare the test treatment to no treatment and to the two reference creams in terms of change in TEWL and redness between days 31 and 29.

The statistical analysis technique used must take account of the design of the study, such that each participant has four 'matched' treatment areas. In addition, the choice of analysis must consider the distribution of the data, as it is likely that both TEWL and redness score will be skewed. Therefore, both transformations combined with parametric tests and non-parametric tests which take account of the 'matched' nature of the data will be considered. Where possible and appropriate the baseline values will be included as a covariate. Further details will be outlined in the SAP.

These analyses will be carried out on the FAS and PPS.

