#### 2.4 Timelines

Analysis will take place once all participants have had their final assessment at Day 31 or have discontinued.

Completion of the SAP, data cleaning and a blind review will take place prior to data base lock. During blind review all decisions about protocol deviations (ITT and PP populations) and analyses (such as assumptions checking) will be made. Once all these activities have taken place then the database will be locked and unblinded.

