# 5. Analysis Sets and Protocol Deviations

**Full Analysis Set (FAS):** All subjects who were diagnosed with a history of AD and were randomised into the study.

**Per-protocol set (PPS):** All participants who are deemed to have no major protocol violations that could interfere with the objectives of this study. This is a sub-population of the FAS.

**Safety set:** All randomised participants who receive at least 1 dose of test or reference cream.

The primary analysis outcome summaries will be performed on both the FAS and the PPS, however the FAS will be considered the primary analysis population . Secondary analyses will be performed on the FAS only.

Safety summaries will be performed on the safety set.

Prior to code breaking, a blind review of the data will be performed. The objective of the review is to identify problems and to make decisions regarding data analytical issues under blind conditions. Important violations of eligibility criteria and other deviations from the protocol will be assessed in cooperation with the Sponsor. Important deviations from the protocol may lead to exclusion of a participant from the PPS. All deviations will be discussed and agreed prior to the unblinding of the data.

In addition the blind data review will consider if the location of observations and the adherence of SLS patches has any impact on the data and if so how to allow for this in the analysis.

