# 7.9 Changes From Protocol

An additional exploratory analysis has been proposed for the blind data review to investigate any impact of the location or adherence of the SLS patches on the observed data at day 31. This is due to investigators noting that the patches may not adhere so well in different locations along the forearm and also that the skin may react differently depending on distance from wrist/elbow.

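### SAP 7.1 leaves test site out of the default primary model with no rule for adding it, and adding it helps only if each contrast also gets its own variance

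*SAP*

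**What the plan says.** Protocol 10.2 allocates treatments by a "randomisation list with balanced allocation to the 4 different test areas (to avoid site-dependent effects"). Each participant therefore carries all four conditions, one per site, and conditions are spread evenly over sites.

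SAP 7.1 models the Day 31 minus Day 29 change with "treatment as a factor, subject as a random effect and day 29 incuded as a covariate". The three key contrasts "will be calculated directly from the ANCOVA model". No site term and no treatment-specific variance is named. If assumptions fail, 7.1 allows transformations or other tests, such as a matched-pairs rank test or a sign test.

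Site appears elsewhere in the SAP only as a matter for the blind review:
- Section 5: "the blind data review will consider if the location of observations and the adherence of SLS patches has any impact on the data".
- Section 7: the data will be explored "to assess if the proposed analysis methods needs to be updated to allow for the location or adherence of the SLS patches".
- Section 7.9 gives the reason: patches may adhere less well in some places, and "the skin may react differently depending on distance from wrist/elbow".
- Section 2.4 places the decision before lock: "During blind review all decisions about protocol deviations (ITT and PP populations) and analyses (such as assumptions checking) will be made".

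None of these gives a test, a threshold, or the form that a site term would take.

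**The concern.** When allocation is balanced on a factor, the treatment estimates are protected from it. If the model omits the factor, however, its variance stays in the residual. Standard errors are then too large for the estimate that the design delivers, tests become conservative, and power is lost. Here the investigators themselves suspect that the factor matters, yet its entry depends on an undefined judgement during data review.

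The obvious remedy, adding site, exposes a second weakness in the same sentence of the plan. The contrasts come from one model with no stated variance structure, while the sample-size section implies that untreated-versus-cream differences vary far more than cream-versus-cream differences. Removing site variance from a single pooled residual narrows every interval, including the one for the lead comparison, which is already too narrow.

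**Working it through.** **Inputs.** SAP 2.3: SD of the paired difference in change is about 8 (untreated vs active) and about 3 (test vs reference); N = 40; target differences 3.5 and 2. SAP 7.5: two-sided 5%. The documents give no site SD. I assume τ = 1, 2 or 3 g/m²/h, the SD of the four site effects.

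**The plan's own figures.** A two-sided paired t-test with N = 40 has 77.0% power for 3.5/8 and 98.4% for 2/3. The second agrees with the plan's claim of more than 90%; the first does not. That shortfall is a separate matter. The figures 77% and 98% are the baseline here.

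**Step 1: omitting site, paired contrasts, τ added to the planning SDs.** Under balance, the squared difference between two sites averages 2τ². The estimated standard error therefore exceeds the site-free one by these factors:
- vs untreated, √(1 + 2τ²/64): 1.016, 1.061, 1.132
- vs reference, √(1 + 2τ²/9): 1.106, 1.374, 1.732

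Simulated power (N = 40, ten random 4×4 Latin squares, no Day 29 covariate; repeat runs agree within about 2 percentage points):

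| τ | vs untreated, without site | with site | vs reference, without site | with site |
|---|---|---|---|---|
| 1 | 77% | 77-78% | 97% | 98% |
| 2 | 74% | 77-78% | 92% | 98% |
| 3 | 69% | 77-78% | 75% | 98% |

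The estimates are unbiased. Type I error without site falls below 5% as τ grows: at τ = 3 it is about 2.5% vs untreated and 0.1% vs reference.

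**Step 2: site already inside the planning SDs.** The SD of 3 then caps τ, because 2τ² ≤ 9 gives τ ≤ 2.1. At τ = 1 to 2, power is about 78% without site and 78-82% with it (vs untreated), and 99-100% either way (vs reference).

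**Step 3: one pooled residual.** Assume SD 8 for all three untreated-cream pairs and SD 3 for all three cream pairs. The pooled within-subject variance is half the mean pairwise variance: (3×64 + 3×9)/6/2 = 18.25.
- Pooled SE for any contrast: √(2×18.25/40) = 0.955.
- True SE vs untreated: 8/√40 = 1.265. With critical value 1.98, rejection under the null needs |Z| > 1.98×0.955/1.265 = 1.495, so type I error is about 13.5%. Simulation gives about 14%.
- True SE cream vs cream: 3/√40 = 0.474. Power for a difference of 2 is P(Z > (1.98×0.955 − 2)/0.474) = P(Z > −0.23), about 59%. Simulation gives about 58%, against 98% for the paired contrast.

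**Step 4: adding site under pooling.** Without site, the pooled SE vs untreated is 0.98/1.05/1.17 at τ = 1/2/3, and type I error is about 13/10/7%. With site, the SE returns to 0.95 and type I error to about 14%. Omitted site variance partly hides the pooling problem, and removing it alone uncovers that problem.

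**Step 5: cost when there is no site effect.** Paired power without vs with site is 76.6% vs 76.3% (untreated) and 98.3% vs 98.2% (reference).

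**The case against.** The strongest reply is that the SAP already names the issue and sends it to a review held before lock and unblinding, so the treatment result cannot steer the choice. That stands. A sensible review would probably also catch a large effect. Under an assumed 5% blind F-test for site, the term enters in about 49-55% of trials at τ = 1 and at least 98% at τ = 2 to 3, and power differs from always including site by at most 0.3 points. No such rule is written, so the Step 1 losses apply only where the review leaves site out.

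The site SDs are assumptions, and SD 8 is an observed SD of raw differences that may already contain site. This also stands. Fixed site differences in resting TEWL cancel in the change score, and the Day 29 covariate, not simulated here, could absorb more. No size can be given for the redness endpoints.

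On variances, the assumption-failure clause in 7.1 could lead to paired tests. It names no trigger and no variance check, so it does not reliably prevent pooling.

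Four stronger readings are tempting, and the documents do not support them:
- That the SAP has no default model. It has one: the written model, without site.
- That the comparisons are biased. Balanced allocation prevents that, apart from imbalance caused by dropouts or lost patches.
- That the protocol demands a site term. Protocol 13.1.4 says "The statistical analysis technique used must take account of the design of the study", but the sentence goes on to the four matched areas per participant, and the subject effect covers matching.
- That every site-level analysis needs the term. SAP 7.9 concerns reactions to the irritant patches at Day 31, not the measurements made before patching.

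**Conclusion.** The point holds as a matter of precision and specification. The default primary model omits the factor on which allocation is balanced, and nothing says when or how it would be added. The cost ranges from nearly nothing (small site effect, site already inside the planning SDs, or an alert review) to about 8 points of power against untreated and 23 against a reference cream (77% to 69% and 98% to 75%, at τ = 3 on top of the planning SDs).

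The variance problem does not depend on the assumed site SD. It rests on applying the SAP's SDs of 8 and 3 to all six treatment pairs, and on reading 7.1 as fitting one common residual variance, which the text does not state but which follows if nothing else is specified. On that basis the lead comparison has a type I error of about 14% with site in the model (7-14% without it), and the cream comparisons lose about 40 points of power (98% to 58%). Site and variance should therefore be settled together.

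**What to change.** In SAP 7.1:

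(a) Prespecify test site (four levels: left or right arm, upper or lower area) as a fixed factor in the primary Day 31 minus Day 29 models, whatever the blind review shows. Leave patch adherence to that review. The same term in the secondary site-level models is optional.

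(b) Estimate each key contrast with its own variance, either through treatment-specific residual variances or through within-subject paired differences adjusted for site. Do not adopt (a) without (b).

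The cost is SAP wording and 3 degrees of freedom, with power essentially unchanged when site has no effect (Step 5). No new data are needed: the product labels carry the randomised site (protocol 10.1.3), and TEWL readings are averaged per site (SAP 6.4).

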## 13.2 Determination of Sample Size

The sample size for this study is based on the primary end point, change in TEWL after induction of skin irritation (change between day 19 and day 21), with the primary comparison being between the test treatment and no treatment and the secondary comparison being between the test treatment and the two reference treatments.

In a similar study the standard deviation of the difference in change in TEWL after induction of skin irritation was seen to be approximately 8 g/m²/h when comparing the no treatment group to an active treatment. (that is: standard deviation of {[Change after skin irritation in no treatment area]-[Change after skin irritation in active treatment area]}).

When comparing the difference between the test treatment and one of the two reference treatments the standard deviation was approximately 3.

If the assumptions of a paired t-test are found to be valid, for a sample of 40 participants this analysis would have >90% power to detect a difference (in change) of 3.5 g/mÇ.h between test treatment and no treatment. The same sample size would also have >90% power to detect a difference (in change) of 2 g/mÇ.h between test treatment and active treatment. If a parametric analysis is indicated then an analysis which includes the baseline as a covariate will be considered which, if there is variation at baseline may increase the power of the analysis further.

If the assumptions of a paired t-test are not met (and a suitable transformation cannot be found) then a sign test (or a wilcoxon matched pairs test) may be used. A power calculation can be carried out for the sign test (46) although this too makes some assumptions. This calculation shows that a sample size of N=40 would have >80% power to detect a difference such that the probability of X>0 (where X is the difference in change, as above) is approximately 0.7. This probability is not unrealistic given the data seen previously, and, if the clinically relevant difference detailed above is seen, the probability of X>0 may in fact be increased leading to higher power. To account for dropouts, 50 subjects will be recruited.

Confidential Page 55 of 65

Version: Version 3.0 Date: 15 August 2019 Sponsor: ACO Hud Nordic AB Study Code: Novum ACO-CT-2018-01 EudraCT No.: 2018-002945-12

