# 2.3 Sample size:

The sample size for this study is based on the primary end point, change in Trans Epidermal Water Loss (TEWL) after induction of skin irritation (change from day 29 to day 31), with the primary comparison being between the test treatment and no treatment and the secondary comparison being between the test treatment and the two reference treatments.

In a similar study the standard deviation of the difference in change in TEWL after induction of skin irritation was seen to be approximately 8 g/mÇ.h when comparing the no treatment group to an active treatment. (that is: standard deviation of {[Change after skin irritation in no treatment area]-[Change after skin irritation in active treatment area]}).

When comparing the difference between the test treatment and one of the two reference treatments the standard deviation was approximately 3.

If the assumptions of a paired t-test are found to be valid, for a sample of 40 participants this analysis would have >90% power to detect a difference (in change) of 3.5 g/mÇ.h between test treatment and no treatment. The same sample size would also have >90% power to detect a difference (in change) of 2 g/mÇ.h between test treatment and active treatment. If a parametric analysis is indicated then an analysis which includes the baseline as a covariate will be considered which, if there is variation at baseline may increase the power of the analysis further.

If the assumptions of a paired t-test are not met (and a suitable transformation cannot be found) then a sign test (or a wilcoxon matched pairs test) may be used. A power calculation

can be carried out for the sign test although this too makes some assumptions. This calculation shows that a sample size of N=40 would have >80% power to detect a difference such that the probability of X>0 (where X is the difference in change, as above) is approximately 0.7. This probability is not unrealistic given the data seen previously, and, if the clinically relevant difference detailed above is seen, the probability of X>0 may in fact be increased leading to higher power.

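### SAP 7.1 reads as one common residual variance for all three TEWL contrasts, although the plan's own SDs for those contrasts are about 8 and about 3; contrast-specific variances should be specified

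*SAP*

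**What the plan says.** SAP 7.1 analyses TEWL change (Day 31 minus Day 29) with a single ANCOVA: treatment as factor, subject as random effect, Day 29 value as covariate. The comparisons of the test cream with no treatment, Miniderm 20% and Diprobase all come from that fit ("Miniderm Novum Vs Diprobase) will be calculated directly from the ANCOVA model"). Neither a covariance structure nor a variance by treatment is given.

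The sizing in SAP 2.3 and Protocol 13.2 uses another analysis and two different SDs:

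- Untreated vs active: "standard deviation of the difference in change in TEWL after induction of skin irritation was seen to be approximately 8" g/m²/h.
- Test vs reference: "When comparing the difference between the test treatment and one of the two reference treatments the standard deviation was approximately 3".
- Stated power at 3.5 g/m²/h vs no treatment: "If the assumptions of a paired t-test are found to be valid, for a sample of 40 participants this analysis would have >90% power".
- Stated power vs a reference: "The same sample size would also have >90% power to detect a difference (in change) of 2" g/m²/h.

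If assumptions fail, SAP 7.1 offers transformations first, and then "alternative tests will be considered, such as the Wilcoxon matched pairs or sign test, and the most appropriate solution applied". Protocol 13.1.4 expects that "it is likely that both TEWL and redness score will be skewed". SAP 2.4 sets the timing: "During blind review all decisions about protocol deviations (ITT and PP populations) and analyses (such as assumptions checking) will be made". That is before lock and unblinding.

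**The concern.** A random subject effect normally comes with one residual variance. In a balanced four-site design, every pairwise contrast then has essentially the same standard error. The plan's own figures imply variances of 64 and 9 for two of these contrasts, a sevenfold difference. One common value cannot suit both.

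Two things are at stake. The comparison ranked first in SAP 4.1, test vs no treatment, would have an interval that is too narrow. The comparison with a reference would have an interval about twice as wide as needed, and the stated power of more than 90% would belong to a different analysis from the one specified.

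**Working it through.** **Inputs.** Two-sided alpha 0.05 (SAP 7.5). SD of the paired difference: 8 (untreated vs active) and 3 (test vs one reference). Differences: 3.5 and 2 g/m²/h. N=40 is the sizing figure and the SAP 2.1 target; N=50 is the protocol's recruitment figure with its dropout allowance. Results are given as N=40 / N=50.

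**1. The plan's figures, paired t-test (noncentral t).**
- Test vs reference, difference 2, SD 3: 98.4% / 99.6%. The stated >90% reproduces.
- Test vs no treatment, difference 3.5, SD 8: 77.0% / 85.8%. The stated >90% does not reproduce. That is a separate matter, but it bears on the cost of the fix.

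**2. One common residual variance.** Four sites have six pairs, and the documents give an SD for only two kinds of pair. *Assumption:* SD 8 for all three untreated–cream pairs and SD 3 for all three cream–cream pairs. The model's variance for any pairwise difference is the mean of the six:

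(3×64 + 3×9)/6 = 36.5 (SD 6.04; residual variance 18.25)

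| | N=40 | N=50 |
|---|---|---|
| Model SE, √(36.5/N) | 0.955 | 0.854 |
| True SE vs reference, 3/√N | 0.474 | 0.424 |
| True SE vs untreated, 8/√N | 1.265 | 1.131 |
| Error df, 3(N−1) | 117 | 147 |
| Critical difference, t × model SE | 1.892 | 1.688 |

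*Power vs reference at 2:* Φ[(2−1.892)/0.474] = 59.0%; Φ[(2−1.688)/0.424] = 76.9%. Simulation (40,000 trials; site variances 59.5 untreated and 4.5 per cream, so 59.5+4.5 = 64 and 4.5+4.5 = 9) gives 59.2% / 76.2%. Power of 90% would need 63 participants.

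*Test vs no treatment:* P(|Z| > 1.892/1.265) = 13.5% / 13.6% type I error by formula, 14.1% / 14.0% simulated. This requires equal means with unequal variances. If all sites are exchangeable under the null, it is about 5%. Coverage needs no null: at a true difference of 3.5 the nominal 95% interval covers 85.9% / 85.9%, against 94.9% / 95.0% paired.

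**3. Range over the unstated SDs.** Keep 8 and 3 fixed. Let each reference vs untreated range over 5–10, and each pair involving the second reference and another cream over 0.5–8, in steps of 0.5. Keep only combinations that form a valid covariance (9,845). The largest power vs the reference is 86% / 94%. Type I error vs no treatment runs from 4% to 24%, so the shortfall in that standard error is not universal either. In the other direction, a second reference that differs from the other creams with SD 8 lowers power to 25% / 43%.

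**4. Day 29 covariate.** The documents give no correlation, so the gain cannot be computed. For illustration, if adjustment multiplies both SDs by √(1−r²) in the like-pair case, 90% power vs the reference is reached at r = 0.60 / 0.44. The ratio of the two SDs does not change, so the error vs no treatment remains.

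**5. If the fallback is used.** SAP 7.1 gives no rule, so one was assumed: a Shapiro–Wilk test on unlabelled residuals. It flags 88% / 94% of simulated trials even when every within-subject difference is normal, because mixing unequal variances makes the pooled residuals look non-normal. What follows depends on the test chosen:

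| After the check | Wilcoxon | Sign test |
|---|---|---|
| Power vs reference at 2 | 93–95% / 98–99% | 87% / 94% |
| Power vs no treatment at 3.5 | 75–78% / 85–86% | 54–59% / 63–65% |

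With Wilcoxon, type I error vs no treatment is 5–7%. A variance-stabilising transformation could not be evaluated, because the plan gives no means.

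**The case against.** The common residual variance is inferred. SAP 7.1 does not rule out treatment-specific variances, and Protocol 13.1.4 requires a method that respects the four matched areas. Sizing by a paired t-test is conditional in the plan, which also foresees a covariate analysis. All of that stands, and it makes this partly a request to state the covariance structure.

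The strongest objection is the fallback. Skew is expected, assumption checks are scheduled before unblinding, and under the check assumed above the pooled model would be dropped about nine times in ten. Wilcoxon would then largely restore power vs the reference. A reader might infer from the 59% that the trial as run will have that power, or that the fallback fails to protect the primary test. The documents support neither. The figures describe the pooled model if it is kept, and the first-listed remedy, transformation, could not be evaluated. Blind review also guards against a choice driven by results.

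What the objection leaves untouched is that a blinded check cannot examine variance by treatment directly. Whether the pooled model is replaced, and by what, is therefore left to a rule not yet written. The power loss also concerns the lower-ranked comparison; for the first-ranked one the issue is coverage and type I error.

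**Conclusion.** The point holds, conditionally. If SAP 7.1 means one residual variance and the model is kept on the raw scale, it conflicts with the plan's own variances of 64 and 9. With like-pair SDs, the interval for test vs no treatment covers about 86%, and its type I error is about 14% if means are equal but variances are not. Power vs a reference at 2 g/m²/h is about 59% (N=40) or 76–77% (N=50).

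These are not fixed properties of the trial. Over the admissible SDs examined, power vs the reference stays below the stated >90% at N=40 without covariate gain, but at N=50 it can exceed 90% in extreme cases. A reader might extend the finding to redness or to the SAP 7.2 models. No SDs are given there, so no error is shown. The matter should be fixed: the remedy is cheap and better matched to the plan's own figures.

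**What to change.** In SAP 7.1, for TEWL change (Day 31 minus Day 29), specify one of the following as primary before unblinding:

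- each key comparison from its own within-subject paired difference, adjusted for the Day 29 difference; or
- a mixed model with unstructured or treatment-heterogeneous within-subject covariance and Kenward–Roger degrees of freedom.

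Secondary point: name one matched fallback test (Wilcoxon matched pairs, for example). Base its trigger on the within-subject differences rather than on pooled blinded residuals, which unequal variances alone can make look non-normal.

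*Cost.* A few lines of SAP text and code. The paired analysis has about 39 error df instead of 117 at N=40. With like-pair SDs, the interval vs no treatment widens from 3.8 to 5.1 (N=40) or from 3.4 to 4.5 (N=50), and paired power at 3.5 is 77% / 86%. The interval vs the reference narrows from 3.8 to 1.9 (N=40) or from 3.4 to 1.7 (N=50).
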